Detailed Protocol Title: Behavior and brain responses to drugs

NCT03964350 Unique Protocol ID: IRB19-0293

Date: 4/11/22

Detailed Protocol Title: Behavior and brain responses to drugs Date: Investigators: [name] Other personnel:

IRB19-0293

Summary: Alcohol abuse and dependence remain significant public health issue, and there is a need to identify risk factors predicting excessive alcohol use. We and others have demonstrated individuals vary widely in their responses to an acute dose of alcohol: Some people experience mainly stimulant-like effects which are generally considered pleasurable, whereas others experience sedative-like effects which are rated more negatively (Holdstock and [name], 1998; King et el 2011). Moreover, the stimulant-like responses to alcohol appear to be predictive of an escalation in use (King 2016). An important question is whether the patterns of stimulant-like and sedative-like subjective effects correspond to differences in brain activation with the drug. We (Weafer et al, 2018) recently reported a good correspondence between stimulant-like subjective response to intravenous alcohol (0.8 g/kg) and activation of ventral striatal brain areas. In the present project, we wish to extend these interesting findings in two ways: i) to examine the dose-relationships between the mood-brain correlations by administering placebo and two doses of alcohol (0.4 and 0.8 g/kg), ii) to investigate the relationship when the drug is administered by the more naturalistic oral route. We propose to assess brain activation patterns in relation to subjective effects using fMRI in a counterbalanced, 3-session, placebo-controlled, double-blind, within-subjects design with placebo, 0.4 g/kg alcohol and 0.8 g/kg alcohol. During an initial drug challenge screening session, 50 potential scanning subjects will receive a single dose of 0.8 g/kg alcohol, to identify individuals who exhibit a pronounced stimulant effect (N=15) or a sedative effect (N=15) from the drug, and only these will participate in the two scanning sessions. We hypothesize that individual variation in the self-reported stimulant or sedative-like effects of alcohol will correspond with variation in activation patterns in reward-related brain regions.

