Design: We will measure individual differences in brain activity after two doses of alcohol (0.4 g/kg, 0.8 g/kg) or placebo using fMRI. Participants (N=50) will first be pre-selected ('ascertained') based on their responses to a single dose of alcohol (0.8 g/kg) in the behavioral laboratory. Individuals who exhibit either a clear stimulant-like response or a clear sedative-like response to alcohol will be invited to continue to the three fMRI scanning sessions. From the 50 participants tested, we will select 15 stimulant responders and 15 sedative responders. The three imaging sessions will be at least 72 h apart. At each session, subjects will receive the beverage containing alcohol or placebo, and then be placed in the fMRI scanner. Order of the three drug conditions (0, 0.4 and 0.8 g/kg ethanol) will be randomized and the drug will be administered under double-blind conditions. Immediately before and after the scan, subjects will complete standardized questionnaires to assess mood and subjective drug effects. We hypothesize that stimulant-like subjective effects will be associated with increases in activation in the striatum and regions related to the mesolimbic dopamine circuit. To minimize variability related to body composition and cycle phase, only males will be recruited for this preliminary study. Later, we will extend the study to include female participants.

Subject Recruitment and Screening

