At the orientation session subjects will read and sign the consent form, which outlines the procedures and lists the classes of drugs subjects might receive and their possible effects. Participants will be informed that they might receive a placebo, stimulant/anorectic, sedative/tranquilizer, opiate/analgesic, alcohol or a cannabinoid/marijuana-like drug. This use of mild deception in this study is necessary to prevent expectancy effects. Subjects will be told the purpose of the study is to investigate the effects of psychoactive drugs upon brain activation. In the consent form subjects agree not to use any drugs except for their normal amounts of caffeine for 24 hours before and 6 hours following each session, and not to operate any machinery requiring concentration for 6 hours following the sessions. They will also agree to fast for 4 hours prior to each session. Participants will also practice completing the questionnaires to be used in the study. They will be allowed to view the fMRI scanners, undergo a mock scan and be instructed on the imaging procedures which will be employed. We will query subjects about any prior history of claustrophobia or anxiety in small spaces. Each subject will complete a detailed questionnaire regarding the presence of any metal implants or metal objects in their body.

Experimental Procedure:

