Subjects will first participate in a 4-hour drug-challenge screening session conducted in the HBPL, where they will receive the 0.8 g/kg dose of ethanol. The purpose of this session is to select 'stimulant responders' and 'sedative responders' to alcohol, and secondarily to ensure that they can tolerate the alcohol dose. Any subjects who experience nausea or other ill effects from the alcohol will be discontinued. Upon arrival at the HBPL, subjects will provide breath and urine samples to detect recent use of alcohol (Alco-sensor III, Intoximeters, St. Louis MO) and drugs (OnTrak TestStik, Roche Diagnostics Indianapolis, IN). Subjects will be instructed that a positive test will result in exclusion from the study. Subjects will complete baseline self-report and drug effect guestionnaires, which will be repeated at 15-30 min intervals throughout the session. Heart rate and blood pressure will be assessed at these same times. After the baseline measures subjects will ingest the dose of alcohol, administered in a gelatin vehicle. Breath alcohol levels (BAL) will be obtained at 15-30 min intervals through the session. Subjects will complete two standardized questionnaires of alcohol effects, the Biphasic Alcohol Effects Scale (BAES; Martin et al, 1993) and the Subjective Effects of Alcohol Scale (SEAS; Morean et al 2013). Both of these include subscales assessing stimulant and sedative effects. Based on their combined responses we will select the 15 subjects who report the greatest stimulant effects and the 15 who report the least stimulant effects from the challenge dose to proceed to the three scanning sessions. Subjects who complete only the initial challenge dose session will receive \$25.

The three scanning sessions will begin in the HBPL for screening measures, and then subjects will be escorted to the Magnetic Resonance Imaging Research Center (MRIRC) for alcohol administration and the fMRI scan. The three sessions will be conducted between 5 and 7pm at least 3 days apart. The end of the session will depend on BAL level; subjects will remain in the laboratory until levels fall below 0.04 g%, as per NIAAA guidelines. Participants will complete the fMRI safety questionnaire to confirm that they do not have any medical condition that

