EPI images will be processed and analyzed using AFNI (Cox 1996), FSL5.0.9 (FMRIB Software Library), and SPM12 (Wellcome Trust Centre for Neuroimaging). The time series will be volume registered to the median image to reduce motion artifact using 3dvolreg within AFNI. Motion outliers will be identified and censored from analyses. Subjects will be excluded if at least one of their scans showed motion >10mm total displacement in any one direction or if more than 50% of volumes within any time point window (see below) were censored. fMRI analyses. Imaging data will be temporally downsampled to the behavioral data by taking a windowed average including the 35 time points before and after the time of the subjective response measurement, resulting in a downsampled dataset at the same temporal resolution as the behavioral data. We chose this relatively long time period because subjective responses are slow-changing, and averaging over a larger window allow for better signal to noise ratio. The windows do not overlap for any time point. The downsampled fMRI data will be voxel wise correlated with the subjective response data (across all time points) using AFNI's 3dfim+, with the resultant coefficients converted to z-scores using Fischer's transformation. The correlation maps will then be coregistered to the participant's anatomical data and warped to MNI space, resampled to 2mm isotropic voxels and smoothed with an 8 mm FWHM isotropic Gaussian kernel.

Further analyses will follow the plan we used in our previous study (Weafer et al, 2019). We compared correlation maps between the time course of subjective response ratings and the time course of BOLD signal following alcohol to those following placebo using paired *t*-tests. In order to control for typical alcohol consumption, we entered average drinks per week

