from the TLFB as a covariate. Based on previous associations between subjective alcohol response and striatal activity, we focused our analyses within three hypothesis-driven anatomically-focused bilateral striatal regions of interest (ROIs): the nucleus accumbens, caudate, and putamen. We also included bilateral primary visual cortex to serve as a negative control ROI. The striatal ROIs were defined via the AAL atlas and created using MARINA (www.bion.de/eng/MARINA.php; Walter *et al*, 2003). The primary visual cortex ROI (Brodmann area 17) was created using the WFU PickAtlas tool (Maldjian *et al*, 2004; Maldjian *et al*, 2003). We extracted parameter estimates/ β weights representing the correlation between BOLD signal and subjective ratings in z-scores from each ROI following alcohol and placebo and conducted paired *t*-tests in SPSS to compare the two drug conditions. We applied a Bonferroni correction across the four ROIs tested, and so the p-value was set at p < 0.0125. We also conducted exploratory, whole-brain analyses of correlations between BOLD signal and stimulation and sedation ratings using SPM12 (cluster-forming voxel-wise height of *p* < 0.001, *k* = 50). Statistical inferences were based on cluster level significance, corrected for family wise error (FWE, *p* < 0.05).

ASL Analysis

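### Dose order is not planned to balance within the two responder groups, and no session term is named, so a first-scan effect would cost precision in the dose contrasts

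*Combined protocol and SAP*

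**What the plan says.** **Order.** The opening Summary describes a "counterbalanced, 3-session, placebo-controlled, double-blind, within-subjects design". The Design section says "Order of the three drug conditions (0, 0.4 and 0.8 g/kg ethanol) will be randomized". No method, block size or stratification is given, and responder group is not mentioned in connection with order.

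**Groups.** From the 50 men challenged, "we will select 15 stimulant responders and 15 sedative responders". Group is fixed before scanning: Experimental Procedure says of the challenge that "The purpose of this session is to select 'stimulant responders' and 'sedative responders' to alcohol". The closing Summary makes the comparison of the two groups the aim of the study.

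**Spacing and familiarization.** "The three imaging sessions will be at least 72 h apart". Under Consenting Procedures, men practise the questionnaires, see the scanner, and "undergo a mock scan and be instructed on the imaging procedures".

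**Analysis.** The fMRI section adopts the plan of the previous study. Correlation maps after alcohol were compared "to those following placebo using paired *t*-tests", and the ROI values were tested with paired t-tests "to compare the two drug conditions". The only covariate named is average drinks per week. The ASL section specifies voxelwise ANOVAs for drug effects. Neither section names session or order, and neither writes out a test between responder groups.

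**The concern.** In a three-session crossover, a man's first scan may differ from his second and third because he is less used to the scanner and to rating himself inside it. The interval between sessions deals with residual alcohol, not with habituation. A paired t-test without session leaves any such effect in the man-to-man spread of the dose differences. Drinks per week cannot absorb it, because it is one value per man and does not vary by session.

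Two things are at stake. The first is the precision of every dose contrast in a study of 30 men. The second is the comparison of 15 stimulant with 15 sedative responders. If one group happens to have more men who receive 0.8 g/kg first, part of its apparent dose effect is a first-scan effect. Balancing order over all 30 men does not prevent that.

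**Working it through.** **Inputs.** From the documents: 30 men (15 + 15), three conditions in three sessions, per-ROI significance level 0.0125. Assumed: two-sided tests, and a first-session shift d of 0.25, 0.5 or 1.0 SD of the paired 0.8-minus-placebo difference. The documents give neither d nor a power calculation.

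**The plan's own figure.** 0.05 / 4 ROIs = 0.0125, which reproduces.

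**Standard error.** A man's difference gains +d if 0.8 g/kg comes first, -d if placebo comes first, and 0 if 0.4 g/kg comes first, each with chance 1/3. The added variance is (2/3)d², so the SE factor is √(1 + (2/3)d²). With exact counterbalancing, 20 of 30 men are shifted and the shifts cancel in the mean, but the estimated SE still grows by √(1 + (20/29)d²).

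**Power.** An effect of 0.645 SD has 80% power with n = 30 and two-sided 0.0125 when there is no session effect (noncentral t). Power and type I error below combine that calculation with a simulation of 20,000 trials per setting.

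| d | SE factor, 2/3 form | SE factor, 20/29 form | Extra men for equal power, (2/3)d² | Power, no session term | Power, first-scan term |
|---|---|---|---|---|---|
| 0.25 | 1.021 | 1.021 | 4% | 78% | 78-80% |
| 0.5 | 1.080 | 1.083 | 17% | 72-73% | 79-80% |
| 1.0 | 1.291 | 1.300 | 67% | 53-54% | 78-80% |

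**Type I error of the dose contrast at nominal 0.0125, no session term.** Simple randomization: 0.012-0.013 throughout. Exact overall counterbalancing: 0.010, 0.008 and 0.0015 for the three values of d. It is never materially above nominal.

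**Between groups.** The chance shift has SD √((2/3)(1/15 + 1/15))·d = √(0.0889)·d = 0.30d, that is 0.075, 0.15 and 0.30. The group contrast's own SE is √(2/15) = 0.365 SD, so at d = 0.5 the shift is 0.149/0.365 = 41% of it. The number of men with 0.8 g/kg first differs between groups by 4 or more in about 17% of simple randomizations and 25% of overall-counterbalanced ones. A group test at nominal 0.05 still has type I error of 0.049-0.052 under both schemes.

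**Within-group balance alone.** With 5 men per Latin-square sequence in each group, the shift between groups is 0. Power of the dose contrast without adjustment remains 73% at d = 0.5 and 53% at d = 1.0. A group test at nominal 0.05 becomes conservative (0.034 and 0.010). The session term is therefore needed as well.

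**Feasibility.** 15/6 = 2.5, so six orders cannot be used equally in a group of 15. 15/3 = 5, so three can.

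**The case against.** The strongest reply is that d may be small. Men have a mock scan and questionnaire practice at orientation, then rate themselves every 15-30 minutes through a 4-hour challenge session. Claustrophobia is an exclusion. The risk section lists scanner anxiety among minor or rare risks and does not contrast first with later scans. At d = 0.25 the loss is about 2 points of power. This stands: the larger losses need d of about 0.5 or more, and nothing in the documents shows that d is that large, or that it is zero.

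The BOLD endpoint also offers some protection. It is a within-session correlation, so a plain first-scan shift in the level of BOLD or of the ratings drops out. Only a change in the coupling between them counts. This stands for BOLD. ASL compares perfusion itself, and the adjustment for global flow leaves regional shifts in place.

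Three stronger readings are tempting, and the documents do not support them:

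- *The order is unbalanced within groups.* The text says counterbalanced in one place and randomized in another, and is silent on responder group. That shows balance is not provided for, not that it is absent.
- *False-positive risk rises.* It stays nominal or falls.
- *First-scan effects bias the group comparison.* The shift is chance imbalance in the one trial that is run, and the error of an ordinary group test already allows for it. The analysis sections contain no written group test for it to invalidate.

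**Conclusion.** The point holds as a cheap improvement in precision, not as a threat to validity. Without a session term, the SE of a dose contrast is about 2%, 8% or 30% wider at d = 0.25, 0.5 or 1.0, and power drops from 80% to about 78%, 72-73% or 53-54%. The group comparison carries an avoidable chance shift with SD about 0.30d.

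These sizes rest on an assumed d, on a shift confined to the first session and common to all men, and on all 30 men completing. The power figures apply to the ROI test at 0.0125. They were obtained with a first-scan term rather than a full three-level session factor, so the power recovered is approximate.

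**What to change.** 1. State one order scheme in both the opening Summary and the Design section, and randomize separately within each responder group from a balanced list. A 3-sequence Latin square with 5 men per sequence is enough. Alternatively, use two sets of all six orders (12 men) plus one Latin square (3 men), with the complementary square in the other group. Each dose then falls in each session 4 + 1 = 5 times per group, and each order is used 2 + 2 + 1 = 5 times over the 30 men.
2. Replace the paired t-tests with a within-man model for the three doses that includes dose and session. Add group and dose-by-group for the stimulant-versus-sedative comparison.
3. Add session to the ASL ANOVA.

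The closing Summary expects dropouts and movement losses, so exact balance may not survive to analysis. The session term protects the dose contrasts when it does not.

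Cost: a new list, held by someone outside the scanning team who knows each man's group; a three-dose model to write in place of a two-condition test, which the three-dose design needs in any case; and two degrees of freedom for session.

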number of subjects. More recently, a study used fMRI to show that oral alcohol suppressed brain activity during performance of simple cognitive tasks (Horn et al. 2006). However, few studies have examined the localized effects of alcohol in the brain in relation to its self-reported subjective effects. As noted above, we recently (Weafer et al, 2018) examined fMRI BOLD response after intravenously administered alcohol. As expected, we found that alcohol produced stimulant-like effects in a subset of individuals, and using region of interest analyses we showed that the time course of stimulation correlated with BOLD signal in the striatum. In the present study we aim to extend this finding i) using more naturalistic, oral administration of ethanol, ii) using two different doses of alcohol, and iii) adding ASL measures to monitor changes in blood perfusion to inform interpretation of neural activation changes. We hypothesize that inter-individual variation in the self-reported subjective effects are expected to be associated with increases in the mesolimbic system (related to dopamine activity), whereas sedative-like effects are expected to be more associated with areas rich in GABA.

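### The stated rule picks the 'sedative responder' group on low stimulation rather than sedation, and the closing Summary makes the same selection on a different scale

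*Combined protocol and SAP*

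**What the plan says.** The protocol describes the second group by sedation in four places. The opening Summary says the challenge session is "to identify individuals who exhibit a pronounced stimulant effect (N=15) or a sedative effect (N=15) from the drug". The Design section says "Individuals who exhibit either a clear stimulant-like response or a clear sedative-like response to alcohol will be invited to continue". Experimental Procedure says "The purpose of this session is to select 'stimulant responders' and 'sedative responders' to alcohol". The closing Summary proposes to compare men with mainly stimulant effects and men with mainly sedative effects, 15 of each.

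The rule itself is in Experimental Procedure. Two questionnaires are given, the Biphasic Alcohol Effects Scale (BAES) and the Subjective Effects of Alcohol Scale (SEAS), and the text notes: "Both of these include subscales assessing stimulant and sedative effects". On the basis of the combined responses, the plan then takes "the 15 subjects who report the greatest stimulant effects and the 15 who report the least stimulant effects".

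The closing Summary gives another rule for the same 15 + 15: the men whose POMS Arousal rises most and least. Dependent Measures lists three questionnaires for the challenge session: BAES, SEAS and the Drug Effects Questionnaire (DEQ). POMS is not among them.

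**The concern.** Ranking men on stimulation and taking both ends gives a high-stimulation and a low-stimulation group. Low stimulation is not the same as sedation: a man who feels almost nothing meets the rule for the lower group but fits none of the protocol's descriptions of a sedative responder. The two effects have separate subscales, and the ranking named uses only one of them.

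The POMS sentence adds a conflict over the instrument. Staff following Experimental Procedure and staff following the closing Summary could invite different men, and neither rule requires sedation.

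At stake are the identity of the 30 men scanned and whether the contrast promised in the closing Summary, mainly stimulant against mainly sedative, is obtained.

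**Working it through.** The plan gives no calculation behind the 15 + 15, so there is no figure of its own to reproduce.

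**1. The text side by side.**

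| Place | Second group is defined by |
|---|---|
| Opening Summary | a sedative effect |
| Design | a clear sedative-like response |
| Experimental Procedure, purpose | being a sedative responder |
| Experimental Procedure, rule | the least stimulant effect |
| Closing Summary, aim | mainly sedative effects |
| Closing Summary, rule | the smallest rise in POMS Arousal |

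Neither rule contains a sedation criterion, and the two rules use different instruments.

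**2. How far low stimulation stands in for sedation.** From the documents: 50 screened, 15 taken from each end. (The recruitment section says forty; 50 is used here, as in both Summaries and Design.) Assumed: stimulation X and sedation Y are standard normal with correlation ρ, that is Y = ρX + √(1 − ρ²)·Z with Z independent of X. Results are averages over 40,000 simulated pools.

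The 15 lowest of 50 on X average -1.14 SD, so their mean sedation is -1.14 × ρ; at ρ = -0.5 this is +0.57.

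| Assumed ρ | +0.5 | 0 | -0.5 | -0.9 |
|---|---|---|---|---|
| Mean sedation of the 15 least stimulated (SD from pool mean) | -0.57 | 0.00 | +0.57 | +1.03 |
| Of those 15, below the pool mean on sedation | 11.0 | 7.5 | 3.9 | 0.6 |
| Of those 15, standardised sedation above standardised stimulation | 11.1 | 12.7 | 14.1 | 15.0 |
| Of those 15, sedation above stimulation if the pool leans to stimulation by 1 SD (assumed) | 4.7 | 8.1 | 10.8 | 13.1 |
| SD of sedation among all 30 selected (pool = 1.0) | 1.07 | 0.99 | 1.07 | 1.22 |

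**3. How far the two rules pick different men.** The same ranking, with an assumed correlation r between POMS Arousal and the BAES/SEAS stimulation score:

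| Assumed r | 0.5 | 0.6 | 0.7 | 0.8 |
|---|---|---|---|---|
| Members who differ, of 15 per group | 7.20 | 6.42 | 5.55 | 4.53 |
| Of the 30 scanned, not scanned under the other rule | 11.03 | 10.47 | 9.65 | 8.44 |

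**4. What a rule using sedation would cost.** Take ranking on X - Y as an example. The correlation of X with X - Y is (1 - ρ)/√(2(1 - ρ)) = √((1 - ρ)/2). The stimulant group's mean stimulation, 1.14 SD under the present rule, becomes 1.14 × √((1 - ρ)/2) = 0.57, 0.81, 0.99 and 1.11 SD at the four values of ρ. With the pool leaning to stimulation by 1 SD, 7.9, 11.7, 13.2 and 13.8 of its 15 'sedative' men have sedation above stimulation. The rank therefore secures relative, not absolute, sedation.

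**The case against.** *Combined responses may include sedation.* The phrase could bring in the sedative subscales, or it could mean only that BAES and SEAS are pooled. No formula is given and the ranking named is on stimulant effects, so the doubt remains.

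*Stimulant and sedative responses are described as contrasting profiles.* The opening Summary and Background do present them so, which fits a negative correlation better than a positive one. If the two effects are strongly opposed, the mismatch nearly vanishes. This limits the size of the problem, but the documents give no correlation and the text still contradicts itself.

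*POMS might be given anyway.* Experimental Procedure refers in general terms to self-report questionnaires, so this is possible. The two rules would still rank on different scales.

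*No planned test uses group.* This stands. A reader might infer that the rule biases a planned p-value. The fMRI section describes paired alcohol-versus-placebo tests, with in-scanner ratings entered as continuous values, and group does not enter them.

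*The sedation prediction does not depend on the groups.* This also stands. Background predicts "whereas sedative-like effects are expected to be more associated with areas rich in GABA", and the exploratory work covers "whole-brain analyses of correlations between BOLD signal and stimulation and sedation ratings using SPM12". A reader might infer that selecting on stimulation starves these of sedation. Under the model above, the spread of sedation among the 30 is about that of the pool or wider.

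A reader might also think the ranked pool is undefined. The closing Summary largely answers this by drawing from the 50 who complete the initial session.

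**Conclusion.** The concern holds as two conflicts in the text: the ranking does not match the group it is meant to fill, and the closing Summary selects the same men on another instrument. That much rests on the wording alone.

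The size rests on assumed correlations, normal scores and equal SDs. It runs from negligible to most of the lower group, depending on how strongly stimulation and sedation are opposed. The choice of scale could change roughly a quarter to a third of the men scanned (8.4/30 = 28% to 11.0/30 = 37%).

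The consequence is confined to who is scanned and to any conclusion about 'mainly sedative' responders. The documents do not support extending it to the validity of the paired tests or to the power of the continuous sedation analysis. It should be fixed, and fixing it is cheap.

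**What to change.** Use one selection rule on one instrument in Experimental Procedure and in the closing Summary. BAES/SEAS is the natural choice because both are already scheduled; the POMS sentence should be removed or reconciled. Then make the rule and the group name agree, in one of two ways.

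- **(a) Keep the stimulant ranking.** Call the lower group 'low-stimulation responders' in the opening Summary, Design, Experimental Procedure and closing Summary. Report each group's change in stimulation and in sedation, and draw no conclusion about sedative responders from group membership. This costs wording only and keeps the full separation on stimulation, but it gives up the sedative-responder label and comparison.
- **(b) Keep the sedative-responder aim.** Add the BAES/SEAS sedative subscales to the rule. No new data are needed. A stimulation-minus-sedation rank is one form; its price is the reduced separation and the merely relative sedation shown in step 4.

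The choice depends on which comparison the investigators want. Under either option, the protocol should note that sedation in the scanner is captured only by the single DEQ item on feeling relaxed or sluggish, since BAES and SEAS are not given there.
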